## 2. Study Objectives

### 2.1 Primary objective

Assess the objective response rate (ORR) to axitinib and avelumab combination according to RECIST 1.1 criteria (Appendix 1) in patients with recurrent or metastatic adenoid cystic carcinoma (ACC) who have evidence of disease progression within 6 months prior to study enrollment.

### 2.2 Secondary objectives

- Assess ORR to axitinib and avelumab combination according to irRECIST criteria patients with recurrent or metastatic adenoid cystic carcinoma (ACC)
- Evaluate median progression free survival (PFS), PFS rate at 6 months after start of treatment
- Evaluate median overall survival (OS), OS rate at 6 months after start of treatment
- Evaluate duration of response (DoR)
- Evaluate safety and toxicity

### 2.3 Exploratory

Assess molecular markers associated with response and resistance to the study combination using tissue and/or plasma obtained from study participants. We hypothesize that studying molecular characteristics of baseline tumor (such as mutational and transcriptional profile), tumor microenvironment (such as immune cells subsets) and serial plasma may reveal biomarkers associated with response to the study combination.

[figure not shown]
## 3. Study Design

### 3.1 Study Design

This is a Phase II, single center open label, study to determine the safety and efficacy of axitinib and avelumab combination in patients with recurrent or metastatic adenoid cystic carcinoma (ACC) with evidence of disease progression within 6 months prior to study enrollment.

Up to 30 patients will be treated with a combination of axitinib 5 mg orally twice a day and avelumab 10mg/kg intravenously every two weeks. A treatment cycle will be 28 days. Treatment will continue until disease progression, death, unacceptable toxicity or consent withdrawal.

### 3.2 Study schema

N=number; Q2W=every 2 weeks; IV=intravenously; PO= per oral; BID=twice a day; Q8W=every 8 weeks

## 4. Study Population

### 4.1 Inclusion criteria

Subjects must meet all the following criteria:

1. Male or female subjects aged  $\geq$  18 years
2. Eastern Cooperative Oncology Group ECOG performance status 0 or 1
3. Histologically confirmed recurrent or metastatic adenoid cystic carcinoma not amenable to curative intent surgery or radiotherapy
4. Measurable disease per RECIST 1.1
5. Evidence of disease progression within 6 months of study enrollment
6. Previously untreated subjects and subject treated with any number of prior lines of therapy are eligible
7. Adequate physiologic function defined as: Hematologic: Absolute neutrophil count (ANC)  $\geq$  1.5  $\times$  10^9/L, platelet count  $\geq$  100  $\times$  10^9/L, and hemoglobin  $\geq$  9 g/dL (may have been transfused). Hepatic: Total bilirubin level  $\leq$  1.5  $\times$  the upper limit of normal (ULN) range and AST and ALT levels  $\leq$  2.5  $\times$  ULN or AST and ALT levels  $\leq$  5  $\times$  ULN (for subjects with documented metastatic disease to the liver). Renal: Estimated creatinine clearance  $\geq$  30 mL/min according to the Cockcroft-Gault formula (or local institutional standard method)
8. Must have archival tissue (Formalin-Fixed, Paraffin-Embedded (FFPE) tissue available-minimum of 15 unstained slides) or be willing to undergo a biopsy
9. For patients receiving antitherapeutic coagulation, patients must be on stable anticoagulant regimen and INR or aPTT must be  $\leq$  1.5 upper limit of normal.
10. Females of childbearing potential must not be breast feeding and must have a negative serum or urine pregnancy test and must agree to use highly effective contraception for a minimum of two weeks prior to receiving study medication until 30 days after discontinuation of the study medication. Acceptable methods of contraception include total and true sexual abstinence, hormonal contraceptives that are not prone to drug-drug interactions (IUS Levonorgestrel Intra Uterine System (Mirena), Medroxyprogesterone injections (Depo-Provera)), copper-banded intra-uterine devices,

and vasectomized partner. All hormonal methods of contraception should be used in combination with the use of a condom by their sexual male partner.

Females of childbearing potential are defined as those who are not surgically sterile (i.e., bilateral tubal ligation, bilateral oophorectomy, or complete hysterectomy) or postmenopausal (defined as 12 months with no menses without an alternative medical cause). Women will be considered post-menopausal if they have been amenorrheic for the past 12 months without an alternative medical cause. The following age- specific requirements must also apply: Women < 50 years old: they would be considered post- menopausal if they have been amenorrheic for the past 12 months or more following cessation of exogenous hormonal treatments. The levels of Luteinizing Hormone (LH) and Follicle-Stimulating Hormone (FSH) must also be in the post-menopausal range (as per the institution). Women ≥ 50 years old: they would be considered post-menopausal if they have been amenorrheic for the past 12 months or more following cessation of all exogenous hormonal treatments, or have had radiation- induced oophorectomy with the last menses > 1 year ago, or have had chemotherapy-induced menopause with >1 year interval since last menses, or have had surgical sterilization by either bilateral oophorectomy or hysterectomy. Patients should refrain from donating eggs from start of dosing until 30 days after discontinuing the study medication.

11. Non-sterilized males who are sexually active with a female partner of childbearing potential must use adequate contraception for the duration of the study and 30 days after the last dose of study medication. Adequate contraception methods include: birth control pills (e.g. combined oral contraceptive pill), barrier protection (e.g. condom plus spermicide, cervical/vault cap or intrauterine device), and abstinence. Patients should not father a child for 6 months after completion of the study medication. Patients should refrain from donating sperm from the start of dosing until 6 months after discontinuing the study medication. If male patients wish to father children they should be advised to arrange for freezing of sperm samples prior to the start of the study medication.

12. For patients with hypertension, upon entry into study must have Blood pressure of <140/90

13. Qtc <470msec.

#### **4.2 Exclusion criteria**

1. Current use of immunosuppressive medication, EXCEPT for the following: a. intranasal, inhaled, topical steroids, or local steroid injection (e.g., intra-articular injection); b. Systemic corticosteroids

at physiologic doses  $\leq$  10 mg/day of prednisone or equivalent; c. Steroids as premedication for hypersensitivity reactions (e.g., CT scan premedication)

2. Active autoimmune disease that might deteriorate when receiving an immuno-stimulatory agent. Patients with diabetes type I, vitiligo, psoriasis, or hypo- or hyperthyroid diseases not requiring immunosuppressive treatment are eligible
3. Prior organ transplantation including allogenic stem-cell transplantation
4. Active infection requiring systemic therapy
5. Known history of testing positive for HIV or known acquired immunodeficiency syndrome
6. Known history of Hepatitis B virus (HBV) or hepatitis C virus (HCV) infection
7. Vaccination within 4 weeks of the first dose of avelumab and while on trial is prohibited except for administration of inactivated vaccines
8. Known prior severe hypersensitivity to investigational product or any component in its formulations, including known severe hypersensitivity reactions to monoclonal antibodies (NCI CTCAE v4.03 Grade  $\geq$  3)
9. Clinically significant (i.e., active) cardiovascular disease: cerebral vascular accident/stroke (< 6 months prior to enrollment), myocardial infarction (< 6 months prior to enrollment), unstable angina, congestive heart failure ( $\geq$  New York Heart Association Classification Class II), or serious cardiac arrhythmia requiring medication.
10. Persisting toxicity related to prior therapy (NCI CTCAE v. 4.03 Grade  $>$  1); however, alopecia, sensory neuropathy Grade  $\leq$  2, or other Grade  $\leq$  2 not constituting a safety risk based on investigator's judgment are acceptable
11. Inadequately controlled hypertension (defined as systolic blood pressure  $>$  140 mmHg and/or diastolic blood pressure  $>$  90 mmHg). Anti-hypertensive therapy to maintain a systolic blood pressure  $<$  140 mmHg and/or diastolic blood pressure  $<$  90 mmHg is permitted.
12. Prior history of hypertensive crisis or hypertensive encephalopathy.
13. Patients with a baseline EKG demonstrating a QTc  $>$  470 ms
14. Serious non-healing or dehiscing wound, active ulcer or untreated bone fracture
15. Proteinuria as demonstrated by urinalysis with microscopy  $>$  150 mg/dL or  $>$  1 g of protein in a 24 hour urine collection. All patients with  $\geq$  150mg/dL protein on urinalysis at baseline must undergo a 24 hour urine collection for protein.
16. Evidence of bleeding diathesis or clinically significant coagulopathy (in the absence of therapeutic anticoagulation)
17. Other severe acute or chronic medical conditions including immune colitis, inflammatory bowel disease, immune pneumonitis, pulmonary fibrosis or psychiatric conditions including recent (within the past year) or active suicidal ideation or behavior; or laboratory abnormalities that may increase the risk associated with study participation or study treatment administration or may interfere with the interpretation of study results and, in the judgment of the investigator, would make the patient inappropriate for entry into this study.
18. Subject with an uncontrolled seizure disorder, active neurologic disease, or active CNS involvement except for individuals who have previously-treated CNS metastases, are asymptomatic, and have no requirement for doses of corticosteroids (indicated to reduce brain edema) higher than the equivalent of 10 mg of oral prednisone a day or anti-seizure medication for at least 2 weeks prior to first dose of study drug.

19. History of ongoing malignancies or malignancies in remission < 2 years. Adequately curative intent treated initial stage non-melanoma skin cancers; in situ carcinoma of the cervix; breast carcinoma in situ; low-grade local bladder cancer; and low-risk prostate cancer undergoing active surveillance will be allowed.

20. Pregnant women are excluded from this study. Based on its mechanism of action. Avelumab can cause fetal harm when administered to a pregnant woman. In animal models, the PD-1/PD-L1 signaling pathway is important in the maintenance of pregnancy through induction of maternal immune tolerance to fetal tissue. Human IgG1 immunoglobulins are known to cross the placenta. Therefore, Avelumab has the potential to be transmitted from the mother to the developing fetus. Blockade of PD-L1 signaling has been shown in murine models of pregnancy to disrupt tolerance to the fetus and to result in an increase in fetal loss. Therefore, potential risks of administering Avelumab during pregnancy include increased rates of abortion or stillbirth. Advise females of reproductive potential to use effective contraception during treatment with Avelumab and for at least one month after the last dose of avelumab.

21. Lactating females: There is no information regarding the presence of Avelumab in human milk, the effects on the breastfed infant, or the effects on milk production. Since many drugs including antibodies are excreted in human milk, advise a lactating woman not to breastfeed during treatment and for at least one month after the last dose of Avelumab due to the potential for serious adverse reactions in breastfed infants.

22. Prior treatment with anti-PD-1 or anti-PD-L1

23. Prior treatment with VEGF or VEGFR inhibitors (e.g. lenvatinib, bevacizumab)

## 5. Treatment Plan

Patients will be treated with a combination of axitinib 5 mg orally twice a day and avelumab 10mg/kg intravenously every two weeks. A treatment cycle will be 28 days. Treatment will continue until disease progression, death, unacceptable toxicity or consent withdrawal.

### 5.1 Axitinib administration

Axitinib will be given at a dose of 5 mg orally twice daily. Axitinib doses will be administered approximately 12 hours apart with or without food and at approximately the same times each day on a continuous schedule. Axitinib should be swallowed whole with a glass of water. If the patient vomits or misses a dose, an additional dose should not be taken. The next prescribed dose should be taken at the usual time. The patient will be requested to maintain a medication diary of each dose of medication. The medication diary will be returned to clinic staff at the end of each cycle. The concomitant use of potent inhibitors of CYP3A4/5 should be avoided. A comprehensive list of strong CYP3A4/5 inhibitors is provided here <http://medicine.iupui.edu/clinpharm/ddis/main-table/> Patients should avoid grapefruit products.

Axitinib will be provided to subjects in tablets (5 mg strength). The tablets will be packaged in appropriate packaging material and stored at room temperature.

Axitinib will be given on days 1 to 28 of a 28-day cycle.

## 5.2 Avelumab administration

Avelumab is a sterile, clear, and colorless solution intended for intravenous (IV) administration. It is presented with a nominal volume of 10 mL at a concentration of 20 mg/mL in single-use glass vials closed with a rubber stopper and sealed with an aluminum polypropylene flip off seal. The vial is intended for single use only.

Avelumab will be administered at 10 mg/kg as a 1-hour IV infusion every 2 weeks (Q2W) on Day 1 and Day 15 of each cycle.

Avelumab will be administered IV on an outpatient basis. Avelumab will be administered in a setting that allows for immediate access to an intensive care unit or equivalent environment and administration of therapy for anaphylaxis, such as the ability to implement immediate resuscitation measures. Steroids (dexamethasone 10 mg), epinephrine (1:1,000 dilution), allergy medications (IV antihistamines), bronchodilators, or equivalents, and oxygen should be available for immediate access.

In order to mitigate infusion related reactions, premedication with Diphenhydramine 50 mg IV, Acetaminophen 650 mg PO and famotidine 20 mg IV 30 to 60 minutes prior avelumab infusions is mandatory. This may be modified based on local treatment standards and guidelines, as appropriate.

Following avelumab infusions, patients must be observed for 30 minutes post infusion for potential infusion related reactions.

## 5.3 Safety assessment

For details see section 6(study calendar and procedures)

1. Blood chemistry and hematology assessments: must be performed at screening, prior to each avelumab dose, at end of treatment visit and at 30 days post-treatment safety follow-up.
2. Urine pregnancy test for women of childbearing potential must be performed at baseline and at least every month during treatment.
3. Free T4 and TSH must be performed at baseline and at least every 8 weeks during treatment and at end of treatment or 30 days post-treatment safety follow-up (if not performed in the previous 8 weeks).
4. Extended safety follow up: give the potential risk of immune-related toxicity, safety follow up will be performed up to 90 days after the last dose of avelumab administration. The extended follow up beyond 30 days after last avelumab administration may be performed either via a site visit or via a telephone call with subsequent site visit requested in case any concerns noted during the telephone call.

## 5.4 Dose Modification

For overlapping toxicities (i.e., toxicities that could be attributed to either avelumab or axitinib), the study PI or co-chair will guide the study co-investigators regarding management on a case by case basis. Decision regarding which drug should be dose reduced/held will be made according to the overall incidence of the adverse event with each individual drug if other factors such as onset of symptoms cannot help define the causative agent. In general, effort should be made to continue

## Proprietary of MD Anderson Cancer Center

axitinib since single agent activity has been reported with this agent in ACC. Guidance for management of the most common overlapping adverse events are outlined below:

- Diarrhea:

Grade 1-2: manage with anti-diarrheal agents (E.g., loperamide). If no improvement dose-reduce/hold axitinib first, if no improvement hold avelumab (management as per Table 4), if improvement, axitinib can be re-started.

Grade  $\geq 3$ : hold both drugs, discard an infectious agent, and treat with anti-diarrheal agents and steroids as per Table 4. Re-start with single agent axitinib.

- Fatigue:

Grade  $\geq 2$ : Hold avelumab first, if no improvement dose-reduce axitinib, if improvement avelumab can be re-started. If only single agent can be tolerated, prioritize axitinib.

- Hypertension

- Hold Axitinib when unable to control blood pressure to  $<140/90$  on greater than 4 Blood pressure medications from multiple classes on maximally tolerated doses.
- Qtc-Hold for  $Qtc > 500$ msec, for  $Qtc$  from 470-499msec, Cardiology collaborator will evaluate and review for drug interactions and presence of underlying structural heart disease, and resume when  $Qtc$  by EKG interpretation shows normal  $Qtc$

- Transaminitis (increase in ALT and/or AST):

Grade 1-2: Hold avelumab first, if no improvement, dose-reduce/discontinue axitinib, if improvement avelumab can be re-started

Grade  $\geq 3$ : hold both drugs, discard an infectious agent, and treat with steroids as per Table 4. Re-start with single agent axitinib.

Other overlapping AEs:

- Decreased appetite, nausea, weight loss, vomiting, dyspnea, arthralgia, stomatitis are more common with axitinib, therefore, dose reductions of these agent should precede avelumab hold.
- Rash, hypothyroidism, asthenia and hematologic toxicities should be initially attributed to avelumab and managed accordingly (Tables 3 and 4), if no improvement by avelumab hold, axitinib dose-reduction/discontinuation should follow.

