#### 5.4.1 Avelumab

Every effort should be made to administer each of the investigational products at the planned dose and schedule. No avelumab dose modifications are permitted in this study, but the next administration of investigational product may be omitted based on persisting toxicity, as outlined in the next tables.

**Table 3.** Treatment Modification for Symptoms of Infusion-Related Reactions

NCI-CTCAE Grade	Treatment Modification for Avelumab
Grade 1 – mild Mild transient reaction; infusion interruption not indicated; intervention not indicated.	Decrease avelumab infusion rate by 50% and monitor closely for any worsening.
Grade 2 – moderate Therapy or infusion interruption indicated but responds promptly to symptomatic treatment (for example, antihistamines, NSAIDs, narcotics, IV fluids); prophylactic medications indicated for $\leq 24$ h.	Temporarily discontinue avelumab infusion. Resume infusion at 50% of previous rate once infusion-related reaction has resolved or decreased to at least Grade 1 in severity, and monitor closely for any worsening.
Grade 3 or Grade 4 – severe or life-threatening Grade 3: Prolonged (for example, not rapidly responsive to symptomatic medication and/or brief interruption of infusion); recurrence of symptoms following initial improvement; hospitalization indicated for clinical sequelae. Grade 4: Life-threatening consequences; urgent intervention indicated.	Stop avelumab infusion immediately and disconnect infusion tubing from the subject. Subjects have to be withdrawn immediately from study drug treatment and must not receive any further study drug treatment.

 
-If avelumab infusion rate has been decreased by 50% or interrupted due to an infusion reaction, it must remain decreased for the next scheduled infusion. If no infusion reaction is observed in the next scheduled infusion, the infusion rate may be returned to baseline at the subsequent infusions based on investigator's medical judgment.
 
- If hypersensitivity reaction occurs, the subject must be treated according to the best available medical practice.
 
	

IV = intravenous; NCI-CTCAE = National Cancer Institute-Common Terminology Criteria for Adverse Event; NSAIDs = nonsteroidal anti-inflammatory drugs.

Table 4. Management of Immune-mediated Adverse Reactions

Gastrointestinal irAEs		
Severity of Diarrhea/Colitis (NCI-CTCAE v4.03)	Initial Management	Follow-up Management

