Grade 3 to 4 Grade 3: Covering $>$ 30% body surface area; Grade 4: Life threatening consequences	Withhold avelumab for Grade 3. Permanently discontinue for Grade 4 or recurrent Grade 3. Consider skin biopsy Dermatology consult 1.0 to 2.0 mg/kg/day prednisone or equivalent Add prophylactic antibiotics for opportunistic infections	If improves to Grade $\leq$ 1: Taper steroids over at least 1 month; resume avelumab therapy following steroids taper (for initial Grade 3).
Pulmonary irAEs		
Grade of Pneumonitis (NCI-CTCAE v4.03)	Initial Management	Follow-up Management
Grade 1 Radiographic changes only	Consider withholding avelumab therapy Monitor for symptoms every 2 to 3 days	Re-assess at least every 3 weeks If worsens: Treat as Grade 2 or Grade 3 to 4.

	Consider Pulmonary and Infectious Disease consults	
Grade 2 Mild to moderate new symptoms	Withhold avelumab therapy Pulmonary and Infectious Disease consults Monitor symptoms daily; consider hospitalization 1.0 to 2.0 mg/kg/day prednisone or equivalent Add prophylactic antibiotics for opportunistic infections Consider bronchoscopy, lung biopsy	Re-assess every 1 to 3 days If improves: When symptoms return to Grade $\leq$ 1, taper steroids over at least 1 month, and then resume avelumab therapy following steroids taper If not improving after 2 weeks or worsening: Treat as Grade 3 to 4.
Grade 3 to 4 Grade 3: Severe new symptoms; New/worsening hypoxia; Grade 4: Life-threatening	Permanently discontinue avelumab therapy. Hospitalize. Pulmonary and Infectious Disease consults. 1.0 to 2.0 mg/kg/day prednisone or equivalent Add prophylactic antibiotics for opportunistic infections Consider bronchoscopy, lung biopsy	If improves to Grade $\leq$ 1: Taper steroids over at least 1 month If not improving after 48 hours or worsening: Add additional immunosuppression (for example, infliximab, cyclophosphamide, IV immunoglobulin, or mycophenolate mofetil)
Hepatic irAEs		
Grade of Liver Test Elevation (NCI-CTCAE v4.03)	Initial Management	Follow-up Management
Grade 1 Grade 1 AST or ALT $>$ ULN to 3.0 $\times$ ULN and/or Total bilirubin $>$ ULN to 1.5 $\times$ ULN	Continue avelumab therapy	Continue liver function monitoring If worsens: Treat as Grade 2 or 3 to 4.
Grade 2	Withhold avelumab therapy	If returns to Grade $\leq$ 1:

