AST or ALT > 3.0 to $\leq$ 5 x ULN and/or total bilirubin > 1.5 to $\leq$ 3 x ULN	Increase frequency of monitoring to every 3 days.	Resume routine monitoring; resume avelumab therapy. If elevation persists > 5 to 7 days or worsens: Treat as Grade 3 to 4.
Grade 3 to 4 AST or ALT > 5 x ULN and/or total bilirubin > 3 x ULN	Permanently discontinue avelumab therapy Increase frequency of monitoring to every 1 to 2 days 1.0 to 2.0 mg/kg/day prednisone or equivalent Add prophylactic antibiotics for opportunistic infections Consult gastroenterologist/hepatologist Consider obtaining MRI/CT scan of liver and liver biopsy if clinically warranted	If returns to Grade $\leq$ 1: Taper steroids over at least 1 month If does not improve in > 3 to 5 days, worsens or rebounds: Add mycophenolate mofetil 1 gram (g) twice daily If no response within an additional 3 to 5 days, consider other immunosuppressants per local guidelines.
Renal irAEs		
Grade of Creatinine Increased (NCI-CTCAE v4.03)	Initial Management	Follow-up Management
Grade 1 Creatinine increased > ULN to 1.5 x ULN	Continue avelumab therapy	Continue renal function monitoring If worsens: Treat as Grade 2 to 3 or 4.
Grade 2 to 3 Creatinine increased > 1.5 and $\leq$ 6 x ULN	Withhold avelumab therapy Increase frequency of monitoring to every 3 days 1.0 to 2.0 mg/kg/day prednisone or equivalent. Add prophylactic antibiotics for opportunistic infections Consider renal biopsy	If returns to Grade $\leq$ 1: Taper steroids over at least 1 month, and resume avelumab therapy following steroids taper. If worsens: Treat as Grade 4.

Grade 4 Creatinine increased > 6 x ULN
	
Permanently discontinue avelumab therapy Monitor creatinine daily 1.0 to 2.0 mg/kg/day prednisone or equivalent. Add prophylactic antibiotics for opportunistic infections Consider renal biopsy Nephrology consult
	
If returns to Grade ≤1: Taper steroids over at least 1 month.

Cardiac irAEs		
Myocarditis	Initial Management	Follow-up Management

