## 9.2 Analysis plan

This is a single-arm, phase II trial to assess the efficacy of the combination of axitinib and avelumab in patients with recurrent or metastatic adenoid cystic carcinoma (ACC) with disease progression within 6 months prior to study enrollment. The primary endpoint is the overall response rate by RECIST 1.1. The trial will be conducted by Simon's 2-stage design and the response rate will be estimated after the second stage (Simon, 1989).

It is assumed that the new regimen will have a target overall response rate at 6 months of 20%. A response rate of 5% or lower is considered a failure and the new regimen will be rejected under this circumstance. When the probability of accepting a "bad" regimen (i.e. ORR $\leq$ 5%) is 0.05 and the probability of rejecting a "good" regimen (i.e. ORR  $\geq$ 20%) is 0.20, Simon's Optimal design requires to enter 10 patients in the first stage. If no patient responds to the treatment, the trial will be stopped and the regimen will be declared as ineffective. If there are one or more responses, 19 more patients will be entered in the study to reach a total of 29 evaluable patients. To ensure that we have 29 evaluable patients we will enroll a total of 30 patients. By the end of the study, the new regimen will be rejected if response rate at 6 months is less than or equal to 3/29 and will be accepted otherwise. The operating characteristics of the trial are given as follows. When the true response rate is 0.05 the probability of stopping the trial early is 60%. On the other hand, if the true response rate is 0.20, the probability to stop the trial early is 10.7%. The expected sample sizes are 17.6 and 27.0 when the true response rates are 0.05 and 0.20, respectively.

To ensure patient safety, the toxicity monitoring will be carried out from the 7th patient using the stopping boundaries calculated based on the beta-binomial distribution. The target toxicity rate by the end of cycle 1 (4 weeks of treatment) is 30%. Toxicity is defined as: as adverse events in the first 4 weeks that are judged to be attributable to one agent or both in combination. Relevant hematological events are grade 4 anemia, grade 4 neutropenia lasting longer than 7 days, febrile

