## Proprietary of MD Anderson Cancer Center

events, including those not identified by laboratory tests, were any grade 3 or worse toxicity except transient ( $\leq 6$  h) grade 3 flu-like symptoms or fever that could be controlled by medical management, transient ( $\leq 24$  h) grade 3 fatigue, local reaction, or headache that resolved to grade 1 or better, grade 3 or 4 nausea and vomiting controlled by optimum medical therapy within 72 h, grade 3 hypertension controlled by medical therapy, grade 3 diarrhea or grade 3 skin toxicity that resolved to at least grade 1 within 7 days of starting medical management (eg, immunosuppressants), any grade 3 or worse amylase or lipase abnormality not associated with symptoms or clinical manifestations of pancreatitis, and tumor flare phenomenon defined as local pain, irritation, or rash localized at sites of known or suspected tumors; grade 3 or 4 increases in alanine aminotransferase or aspartate aminotransferase concentrations concurrent with grade 2 increase in total bilirubin concentration (liver function); non-hematological grade 3 or worse laboratory abnormality that needs medical intervention or led to hospital admission (excluding single laboratory values out of normal range judged unlikely to be related to trial treatment by the investigator, without clinical correlates, and that resolved to grade  $\leq 1$  within 7 days with adequate medical management); and any event related to the trial treatment preventing completion of at least 75% of doses of axitinib or two infusions of avelumab during the first cycle of combined therapy. The prior probability of toxicity for the regimen is modeled by a beta distribution Beta (0.3, 0.7). The following decision criteria will be applied:

stop if  $\text{Prob}\{\theta_{\text{TOX}} > 0.30 \mid \text{data from the trial}\} > 0.7$

Patients recruited will be monitored continuously according to the following stopping boundaries for toxicity.

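### For a grade 1 ALT/AST rise that either drug could cause, section 5.4 holds avelumab while Table 4 continues it, and a day-15 hold can put a grade 1 laboratory value into the toxicity count (minor)

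*Combined protocol and SAP*

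**What the plan says.** **Section 5.4 (Dose Modification)** covers toxicities that either drug might have caused. For these, "the study PI or co-chair will guide the study co-investigators regarding management on a case by case basis". For transaminitis the guidance reads "Grade 1-2: Hold avelumab first, if no improvement, dose-reduce/discontinue axitinib", with avelumab restarted on improvement. The line for grade 3 or worse refers to Table 4; the grade 1-2 line does not.

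**Table 4 (section 5.4.1), hepatic grade 1**, covers ALT or AST above ULN to 3.0 x ULN. Avelumab continues, and the follow-up column says "Continue liver function monitoring If worsens: Treat as Grade 2 or 3 to 4". The first hold is at grade 2, with the instruction "Increase frequency of monitoring to every 3 days". Once the value is back to grade 1 or lower, the instruction is "Resume routine monitoring; resume avelumab therapy".

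**Section 5.4.1** asks for dosing on schedule wherever possible and adds that "the next administration of investigational product may be omitted based on persisting toxicity, as outlined in the next tables".

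**Section 9.2** monitors toxicity, defined as "adverse events in the first 4 weeks that are judged to be attributable to one agent or both in combination". One listed criterion is any treatment-related event "preventing completion of at least 75% of doses of axitinib or two infusions of avelumab during the first cycle". That criterion has no minimum grade.

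**The concern.** Two instructions in the same section give opposite actions for the same laboratory value. Section 5.3 requires chemistry before each avelumab dose, and section 5.2 schedules cycle 1 infusions on days 1 and 15, so the day-15 infusion is decided on that value.

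The choice matters for the safety monitoring. If the infusion is given, an isolated grade 1 rise is not a toxicity. If it is held and not made up within cycle 1, the missed-infusion criterion can count the patient. The other laboratory and liver criteria in section 9.2 start at grade 3 (with grade 4 for some blood counts), and even grade 3 amylase or lipase rises without symptoms are excluded. Counting a grade 1 ALT therefore looks unintended. The exclusion for single out-of-range laboratory values is attached to the grade 3 or worse laboratory criterion, so it does not clearly remove these cases.

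**Working it through.** **1. The texts side by side, grade 1 ALT/AST**

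| Source | Trigger | Avelumab |
|---|---|---|
| Section 5.4, transaminitis | Grade 1-2, either drug a possible cause | Hold |
| Table 4, hepatic grade 1 | Liver-test grade (above ULN to 3.0 x ULN) | Continue, monitor |
| Table 4, hepatic grade 2 follow-up | Back to grade 1 or lower | Resume |
| Section 4.1, criterion 7 | ALT/AST at or below 2.5 x ULN (5 x ULN with liver metastases) | Eligible to start |

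The 2.5 x ULN entry limit lies inside the grade 1 band. A patient may start avelumab at 2.5 x ULN, or resume it at grade 1 after a grade 2 episode, yet has it held for a new grade 1 rise of unclear cause. Grade 2 is held under both texts, so the conflict over holding is confined to grade 1.

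**2. Path into the toxicity count.** All of these must occur:
- a grade 1 rise on the day-15 test, with either drug a possible cause;
- the section 5.4 hold is applied;
- the value is recorded as an adverse event (section 7.1.1 refers to clinically significant laboratory findings);
- it is judged treatment-related;
- the infusion is not given later in cycle 1.

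On the last condition, section 5.4 sets no recheck time, and the three-day recheck in Table 4 begins at grade 2. The next scheduled chemistry is nominally day 15 + 14 = day 29, in cycle 2. Section 6.1 permits earlier tests.

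**3. Reproducing the plan's figures.** Inputs from section 9.2: prior Beta(0.3, 0.7); stop if P(theta > 0.30 | data) > 0.7; first look at 7 patients. With x toxicities in n patients the posterior is Beta(0.3 + x, 0.7 + n - x). The smallest x that crosses 0.7 matches Table 8 at every n from 7 to 29.

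For the chance of early stopping, let f_n(x) be the probability of reaching n patients with x toxicities without having stopped. Then f_n(x) = p f_{n-1}(x-1) + (1-p) f_{n-1}(x), and mass at or above the Table 8 limit is removed at each look.

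| True rate | Table 9 | Recomputed |
|---|---|---|
| 0.1 | 0.032 | 0.0318 |
| 0.2 | 0.225 | 0.2253 |
| 0.3 | 0.584 | 0.5841 |
| 0.4 | 0.876 | 0.8758 |
| 0.5 | 0.982 | 0.9824 |

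Looks at 7 and then every 3 patients give the same values. The monitoring arithmetic is correct; the question is only which events enter it.

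**4. One extra counted event at the first look (n = 7)**
- x = 2: Beta(2.3, 5.7), P(theta > 0.30) = 0.426, continue.
- x = 3: Beta(3.3, 4.7), P(theta > 0.30) = 0.729, stop.

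Suppose one of the first 7 patients has met every condition in step 2 and has no other toxicity. Let p be the assumed toxicity rate in the other 6. The trial stops with at least 2 of 6 if that patient counts, and with at least 3 of 6 if not.

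At p = 0.20:
- P(at least 2 of 6) = 1 - 0.8^6 - 6(0.2)(0.8^5) = 1 - 0.2621 - 0.3932 = 0.345.
- P(at least 3 of 6) = 0.3446 - 15(0.2^2)(0.8^4) = 0.3446 - 0.2458 = 0.099.

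| Assumed p | Counted | Not counted |
|---|---|---|
| 0.10 | 0.114 | 0.016 |
| 0.20 | 0.345 | 0.099 |
| 0.25 | 0.466 | 0.169 |

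**5. Whole trial, for assumed increments.** If such holds added 0, 2 or 5 percentage points to the toxicity rate, early stopping would be:

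| Rate from other causes | +0 | +2 | +5 |
|---|---|---|---|
| 10% | 0.032 | 0.054 | 0.102 |
| 20% | 0.225 | 0.289 | 0.396 |

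The increments have no source in the documents. For scale only, Table 2 (section 1.4) gives 16 of 55 patients with related ALT increases, 4 of them grade 3, leaving 16 - 4 = 12 of 55 (22%) at grade 1-2. That is over a median of about 36 weeks on treatment. Five points would need 5/22, nearly a quarter of such patients, to be grade 1 on day 15 and not re-dosed within the cycle.

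**The case against.** The strongest reply is that the documents largely settle the matter. A rise of unclear cause is exactly what section 5.4 covers, Table 4 is headed for immune-mediated reactions, and section 5.4 refers to Table 4 where it wants it. Leaving Table 4 out of the grade 1-2 line may be deliberate. The PI or co-chair guides these cases, in a single-center trial. There is also a reason for caution: in the earlier combination study ALT increase was the only event that led more than one patient to stop avelumab (3 of 55).

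Much of this stands. A reader might infer that the plan gives no guidance at all on which text applies; it does give some, and it points to section 5.4. What remains is that no sentence states precedence, the hepatic rows of Table 4 are keyed to liver-test grade, and section 5.4.1 ties omitted doses to the tables. If section 5.4 governs, the result is the odd one in step 1, and the counting path is open. If discretion governs, similar patients may be counted differently against a fixed boundary.

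A reader might also infer that the line defeats the stated aim of keeping patients on axitinib. The documents do not support that strongly: avelumab is held first, and axitinib is touched only if there is no improvement.

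Finally, the reply notes that the root of the counting problem is the missing grade floor in section 9.2, and that the texts also differ on a persistent grade 2 rise, which Table 4 escalates to grade 3-4 management after 5 to 7 days. Both are true, and the proposed change leaves both as they are.

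**Conclusion.** The inconsistency at grade 1 is real and worth correcting, but minor. Holding avelumab when its role is uncertain while continuing it when the rise is judged immune-mediated does not fit the entry limit or the resumption rule. The same line lets a grade 1 laboratory value enter the toxicity count, provided every condition in step 2 holds.

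A reader might infer from 0.345 against 0.099 that this wording materially raises the trial's risk of stopping. The documents do not support that. Those figures assume that the whole chain has already occurred in one of the first seven patients, and a 20% rate in the others. The frequency of related grade 1 rises on day 15 is not given, so the expected effect cannot be computed. Tables 8 and 9 themselves are correct.

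**What to change.** In section 5.4, split the transaminitis grade 1-2 line in two. Grade 1: continue both drugs and monitor as per Table 4. Grade 2: the present instruction unchanged, that is, avelumab held first, axitinib reduced or discontinued if there is no improvement, and avelumab restarted if there is. The rest of section 5.4 stays as it is.

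The cost is one line in a protocol amendment, with no new data, visits or patients. The downside is a slightly less cautious response to grade 1 rises. Chemistry before every avelumab dose and the hold at grade 2 cover this. The change adds no grade floor to section 9.2, so a related grade 2 hold that costs the second infusion would still count as a toxicity.
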